Randomized Controlled Trial of Ultrasound-guided Fluid Resuscitation of Sepsis-Induced Hypoperfusion and Septic Shock

NCT identifier 03020407

Updated 1 October 2020

Study Protocol

In our protocol we prepared the preplanned, permuted block-of-four randomization list that was blinded to the investigators before patient allocation. Randomization was set at a 1:1 ratio of the ultrasound-guided and usual-care arms. When an eligible patient was identified and informed consent was obtained, demographic data, preexisting condition, bloodwork, diagnostic investigations, microbiologic workups, and blood lactate were collected at ED arrival (hour 0). Prompt empirical antibiotics were given to every patient within one hour after ED arrival. Then, the patient was rapidly assigned in accordance with the randomization and treated with one of the two treatment strategies as follows:

Ultrasound-guided fluid management (UGFM) strategy

In this treatment arm, the treating emergency physician promptly assessed the IVC diameter to obtain the IVC collapsibility index (IVCCI) (or distensibility index, IVCDI; see below for the description, formulation and measurement method) of each patient while venous access was performed and initial laboratory specimens were collected. A previous study showed that IVCCI $> 40\%$ was strongly associated with fluid responsiveness. 24 Accordingly, the patient was given a 10 milliliters (mL)/ kg bolus of 0.9% normal saline solution (NSS) without delay if an IVCCI $> 40\%$ was discovered, and serial measurements were immediately performed after each IV bolus was achieved an IVCCI $< 40\%$ during our protocol. Then, the rate of IV fluid administration was maintained based on the individual's condition. If the patients in this arm subsequently required endotracheal intubation and MV with sedation within six hours after initiation of therapy, the IVCDI was measured as a replacement for IVCCI. The same amount of NSS was given when IVCDI $> 18\%$ 17 until IVCDI $< 18\%$ was achieved. The IVC evaluation was serially performed and recorded every two hours until six hours after ED presentation. The same treatment protocol was repeated when the threshold of IVCCI (or IVCDI) percentage for potential fluid responsiveness was identified.

Inferior vena cava diameter measurement and indicators of fluid responsiveness

In our protocol, IVC was identified in longitudinal section in the subcostal area using the curvilinear or phased array transducers (cardiac) of a standard ultrasound machine. The selected area of IVC diameter measurement was set at 2 centimeters distal to the confluence of the hepatic vein by M-mode coupled with two-dimensional mode on frozen screen images using the Sonosite X-porte (Fujifilm Sonosite, Inc., Bothell, WA). All treating physicians including attending staff and residents regularly participated in hands-on training twice a year (as usual basis) by a qualified international instructor in critical care ultrasonography (the third author). The residents who were allowed to perform the study protocol required at least six months

exposure in real clinical experience and had passed formal performance evaluation on ultrasonographic IVC measurement. If the patient was breathing spontaneously, the IVCCI, which reflects the decrease in IVC diameter on spontaneous inspiration, was used. IVCCI is calculated as follows:

$$[(\text{IVC diametermax} - \text{IVC diametermin}) / \text{IVC diametermax}] \times 100\%.$$

If the patient required MV for respiratory support, the IVCDI, which reflects the increase in IVC diameter on mechanical inspiration, was used. IVCDI is calculated as follows:

$$[(\text{IVC diametermax} - \text{IVC diametermin}) / \text{IVC diametermin}] \times 100\%.$$

Sample images of ultrasonographic landmark and respirophasic diameter changes of an IVC during volume expansion are shown in Figures S1A and S1B in the Supplemental material.

Usual-care strategy

Patients were promptly treated with 30 mL/kg loading of NSS in this treatment arm. After the NSS bolus, treatment with either the additional IV fluid or a vasopressor was given at the physicians' discretion during the six-hour study period. The threshold for the need of a vasopressor was set at mean arterial pressure below 65 mm Hg if a patient did not respond to fluid therapy during each treatment protocol, and the time of vasopressor administration was noted. However, ancillary fluid administration was allowed at treating physicians' judgment in both treatment arms. Other adjunctive therapies, such as colloid administration, central venous catheterization, or surgical removal of the infectious source, were not prohibited in our protocol and were used at the discretion of the treating physicians. The study patients were closely monitored while we recorded their clinical parameters every two hours for study purposes. Our resuscitative study protocol stopped at six hours after initiation of the treatment. After this period, patients were treated according to the physicians' judgment.

Outcome Measurements

At six hours after treatment, the cumulative fluid volume was recorded, and blood lactate was obtained for lactate clearance calculation. At 72 hours after ED presentation, the cumulative fluid volume from the initial presentation was again recorded, and the patients were followed for clinical condition evaluation and blood chemistry tests to calculate the SOFA score and assess its change from the hour-zero baseline. The in-hospital requirement and time to start renal replacement therapy or MV were followed and recorded by searching the electronic data summary of a patient. The indication to initiate these life-saving procedures was at the discretion of the treating physicians. To identify the deceased patients for mortality analysis, we retrieved the electronic database of in- and outpatient clinical records or made a telephone call to the patients or their personal contact in every case at 30 days after the day of hospital presentation. The clinical data retrieval was performed and recorded by the trained non-investigators.

Data Analysis

Sample-size determination

According to the results of large trials of septic shock treatment, the 90-day mortality was 30% in the usual-care group.⁹⁻¹¹ Based on this information, we calculated that a sample of 254 patients would have a power of 80% to detect a relative reduction of 50% in risk (15 percentage points of absolute risk reduction) in the UGFM group, allowing for a loss to follow-up or withdrawal of 5%. The target number for primary outcome analysis would be 121 patients per

group. One interim analysis was performed after the enrollment of 50% of the patients, with the use of a two-sided symmetric O'Brien–Fleming (or alpha spending method) design.

Statistical analysis

We used Stata version 14.0 (StataCorp LLC, College Station, TX) for all statistical tests and production of graphics. The normally and non-normally distributed data were analyzed using the two independent-samples t test and Mann-Whitney U test, respectively. A χ^2 test with odds ratio (OR) was performed to compare the proportions between the groups. No data were imputed for any missing information. We used the Kaplan-Meier curve and the log-rank test to compare the 30-day mortality between the treatment arms. All tests were two-sided for superiority testing and considered statistically significant at a $p < 0.05$.

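### Fixed blocks of four with arms visible at the bedside leave part of the sequence deducible in principle, and no planned mortality analysis uses hour-0 severity

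*Combined protocol and SAP*

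**What the plan says.** The opening paragraph of Study Protocol describes the allocation: "we prepared the preplanned, permuted block-of-four randomization list that was blinded to the investigators before patient allocation". The ratio is 1:1. No second block size and no stratification factor is mentioned. Consent comes first ("When an eligible patient was identified and informed consent was obtained"), then the hour-0 data, then assignment ("Then, the patient was rapidly assigned in accordance with the randomization").

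The treating team can see the arm. Under the UGFM strategy, "the treating emergency physician promptly assessed the IVC diameter" and repeats the scan over six hours. Under Usual-care strategy, "Patients were promptly treated with 30 mL/kg loading of NSS in this treatment arm". The section on IVC measurement refers to "All treating physicians including attending staff and residents", so more than one physician treated patients.

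Statistical analysis plans a chi-square test with an odds ratio for proportions, and Kaplan-Meier curves with a log-rank test for 30-day mortality. No covariate, stratum or regression model appears, and missing values are not imputed. Lactate is measured at hour 0 (Study Protocol). Outcome Measurements uses 72-hour data to "calculate the SOFA score and assess its change from the hour-zero baseline", so SOFA at hour 0 is available too. The plan uses these two baseline values only for lactate clearance and SOFA change.

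**The concern.** Concealing a list protects its future entries from being read. It does not protect them from being inferred. In a 1:1 block of four, the fourth assignment is fixed by the first three, and the third is fixed when the first two match. If past assignments are visible, someone who keeps count can foresee some of the next ones.

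Taking consent before assignment limits this but does not remove it, because the decision whom to approach comes earlier. If a foreseen arm influenced that decision, baseline risk could differ between arms, and an unadjusted mortality comparison would carry the difference into the result. No planned analysis would show whether the mortality finding survives allowance for measured severity, although the variables needed are already collected. Apart from selection, leaving out strong baseline predictors also gives up some precision.

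**Working it through.** **1. The plan's own figure.** Inputs from Sample-size determination: 30% against 15%, 80% power, 5% loss. Statistical analysis gives two-sided 0.05. With the pooled two-proportion formula and mean rate 0.225:

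n = [1.960 × √(2 × 0.225 × 0.775) + 0.842 × √(0.30 × 0.70 + 0.15 × 0.85)]² / 0.15² = 120.5, so 121 per group.

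242 × 1.05 = 254.1 and 242 / 0.95 = 254.7. The stated 121 and 254 are reproduced, and this point does not affect them.

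**2. Ceiling on predictability.** A 1:1 block of four has 6 equally likely orders, hence 24 positions. The fourth is determined in all 6 orders and the third in 2 of 6, so 8/24 = 33% are known for certain. The best guess is right in 17/24 = 71% of positions, against 50% with simple randomisation. 254 patients make 63 full blocks plus 2, and 63 × 4/3 = 84 certain allocations.

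**3. Incomplete observation.** Let each earlier assignment be seen with assumed probability p.

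- *Boundaries still known.* An allocation is certain only if both earlier patients of the exhausted arm were seen, which gives p²/3.
- *Number missed unknown.* Simulated lists of 254, with an exact Bayesian update over the position in the block.

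| | p = 0.75 | p = 0.5 | p = 0.25 |
|---|---|---|---|
| Certain, boundaries known | 19% | 8% | 2% |
| Certain, number missed unknown | 0% | 0% | 0% |
| Best guess, number missed unknown | 63% | 59% | 55% |

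**4. Undisclosed random blocks of 4, 6 and 8 (simulated).** With full tracking, about 2% are certain and the best guess is 68%. With the number missed unknown, 0% are certain and the best guess is 61%, 57% and 54%. The gain is almost wholly in certain knowledge.

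**5. Worst-case illustration.** Assumptions not in the documents: mortality is 30% with no treatment effect, and every foreseen patient is selected, always in favour of UGFM. Risk is d points lower than average in foreseen UGFM patients and d points higher in foreseen usual-care patients. A shift of d is therefore a gap of 2d points between foreseen patients in the two arms. With a fraction f foreseen, bias = 2 × f × d, and SE = √(2 × 0.3 × 0.7 / 121) = 5.89 points.

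| d (gap 2d) | Bias, f = 1/3 | Type I error, f = 1/3 | Type I error, f = 1/12 |
|---|---|---|---|
| 2 (4) | 1.3 | 5.6% | 5.0% |
| 5 (10) | 3.3 | 8.7% | 5.2% |
| 10 (20) | 6.7 | 20.5% | 5.9% |

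f = 1/3 is full tracking. f = 1/12 is p = 0.5 with known boundaries.

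**6. Precision forgone.** The documents give no prognostic strength. If hour-0 severity explained an assumed 0%, 10% or 20% of outcome variance, the number per group for the same power on the risk-difference scale would be 121 × 1.0, 0.9 or 0.8 = 121, 109 or 97. In a simulation with an assumed severity log-odds SD of 1.0, adjustment raised power from about 80% to 84%.

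**7. Scale.** At 30% against 15% the marginal odds ratio is (0.15/0.85)/(0.30/0.70) = 0.41. With perfectly balanced arms and an assumed severity log-odds SD of 0.5, 1.0 or 1.5, the conditional odds ratio is 0.40, 0.36 or 0.31. That gap is not corrected imbalance.

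**8. Deaths available.** The sample-size section gives only a 90-day rate, so 30-day control rates of 15%, 20% and 30% are assumed. With the full 50% reduction, 121 × 1.5 × rate = 27, 36 and 54. With no effect, 242 × rate = 36, 48 and 73. For three parameters (arm, SOFA, lactate) the extremes are 27/3 = 9 and 73/3 = 24 deaths per parameter.

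**The case against.** The strongest reply is that nothing here is wrong. Permuted blocks of four, a concealed list and consent before assignment form a recognised scheme, and unadjusted chi-square and log-rank tests are valid under sound randomisation. That stands.

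The reply continues that the mechanism needs facts the documents do not give: who recruited, who held the list, and whether recruiters knew the block size and boundaries or saw every assignment. That stands too. A reader might infer that a third of the allocations were in fact predictable, or that selection took place. The documents support neither: 33% describes an ideal observer whom they do not show to have existed. Several physicians treated patients, and an observer who lost count could foresee nothing with certainty. Nor should the 20.5% be read as an estimate, since it needs full tracking, selection of every foreseen patient, one constant direction and an assumed 20-point gap.

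A reader might also infer that the unadjusted tests fail because chance can leave the arms unequal in severity. They do not: their type I error already covers chance imbalance, and adjustment there buys precision rather than validity.

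Finally, varying the block size barely lowers guessing accuracy (71% to 68% with full tracking), and the past tense of the text suggests that allocation may be complete. Both limit the first part of the remedy. Neither touches the second: an adjusted estimate can still be obtained from data already collected, and without it the reader cannot judge robustness to measured severity.

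**Conclusion.** The point holds as a minor weakness of robustness and efficiency. With one named block size and visible arms, blinding the list is not by itself enough to keep later allocations unforeseeable. The certain share lies between 0% and a ceiling of 33% (about 84 of 254), depending on what an observer knew and saw, and the documents do not settle that. The bias figures rest entirely on assumed shifts and an assumed 30% mortality. At half-visibility with known boundaries, even the largest assumed shift moves type I error only to 5.9%.

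The planned mortality tests are valid if randomisation was sound, and the sample size is unaffected. What they lack is protection against a selection-induced difference in severity and use of the precision in hour-0 SOFA and lactate. An adjusted analysis would address measured severity only and could not rule out selection on unmeasured prognosis.

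**What to change.** **Allocations still to be made, if any.** Use randomly varying, undisclosed block sizes (for example 4, 6 and 8), generated outside the treating team. This cuts certain knowledge under full tracking from 33% to about 2%. The cost is regenerating the rest of the list and a temporary imbalance of up to four patients rather than two. In either case, report whether the block size was withheld from recruiting physicians.

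**Analysis.** Keep the unadjusted comparison as primary. Add one sensitivity analysis: logistic regression of 30-day death on arm, hour-0 SOFA and log hour-0 lactate, labelled post hoc if it is added after data are seen.

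- Report a standardised (marginal) risk difference and a marginal odds ratio, with the number analysed, beside the unadjusted estimates in the same patients. A conditional odds ratio should not be set against the unadjusted one.
- State in advance a minimum number of deaths below which only SOFA is used.

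The cost is one model from data already collected and no larger sample. Because missing values are not imputed, anyone lacking hour-0 SOFA or lactate drops out of this analysis.

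### Lactate clearance starts at ED arrival but ends six hours after treatment, so its length varies by patient and could differ by arm

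*Combined protocol and SAP*

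**What the plan says.** **First sample.** The Study Protocol section lists what was collected once a patient was eligible and had consented: "demographic data, preexisting condition, bloodwork, diagnostic investigations, microbiologic workups, and blood lactate were collected at ED arrival (hour 0"). Antibiotics come next ("Prompt empirical antibiotics were given to every patient within one hour after ED arrival"), and then allocation: "Then, the patient was rapidly assigned in accordance with the randomization". Treatment under one of the two strategies follows.

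**Second sample.** Outcome Measurements: "At six hours after treatment, the cumulative fluid volume was recorded, and blood lactate was obtained for lactate clearance calculation".

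**The six-hour period.** The Usual-care strategy section gives its end: "Our resuscitative study protocol stopped at six hours after initiation of the treatment". The UGFM strategy section uses another anchor for the scans: "The IVC evaluation was serially performed and recorded every two hours until six hours after ED presentation".

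**Start of treatment.** Usual care opens with a fixed fluid load, given promptly. UGFM opens with a scan of the inferior vena cava, done "while venous access was performed and initial laboratory specimens were collected", and a bolus follows only if the index exceeds its threshold.

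**Analysis.** Statistical analysis provides a two-sample t test or a Mann-Whitney test for continuous data. No covariates are named. The plan gives no formula for lactate clearance, no sampling window and no rule about interval length.

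**The concern.** Clearance is a change over time, so it depends on how long the change was allowed to run. Here the start is fixed to arrival and the end to treatment. Any wait between the two lengthens the interval, and an unadjusted comparison takes no account of it.

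Variation in the wait that is common to both arms adds noise but no bias. A wait that differs systematically between arms is more serious, because it could show up as a difference in clearance when the treatments have the same effect. This design leaves room for that. One arm starts with fluid for everyone. The other starts with a scan whose result decides whether a bolus is given, and the plan does not say which of these events starts the six-hour clock. If the bolus starts it, a UGFM patient below the threshold has no defined start time.

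The stake is the interpretation of one early outcome. The sample size rests on mortality and is not affected.

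**Working it through.** The plan states no figure for lactate clearance, so there is none to reproduce. The check is of the timing, followed by an illustration of size.

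**Step 1: the interval.** Two readings are needed. The hour-0 lactate is taken as the clearance baseline, since no other earlier lactate is described. Six hours after treatment is taken to mean after initiation of treatment, as in the sentence that ends the protocol period. With d the time from ED arrival to treatment start:

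interval = 6 h + d

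The Study Protocol section places consent, hour-0 sampling and assignment before treatment, so d is not zero by definition. No maximum for d is given; the text says only that assignment was rapid.

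**Step 2: the clocks.**

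| Event | Clock |
|---|---|
| First lactate | ED arrival |
| Second lactate | Treatment |
| End of protocol period | Initiation of treatment |
| End of serial scans | ED presentation |

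The plan uses two anchors for its six-hour marks and does not reconcile them.

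**Step 3: size if lactate falls from arrival onward.** Assume exponential decline at one rate throughout, with true six-hour clearance c of 20% or 30%:

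k = −ln(1 − c)/6; measured clearance = 1 − exp(−k(6 + d))

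For c = 20%, k = 0.2231/6 = 0.0372 per hour. For c = 30%, k = 0.3567/6 = 0.0594 per hour.

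**Step 4: size if lactate rises before treatment.** Assume a rise of 5% per hour until treatment, then clearance c over the six treated hours:

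measured clearance = 1 − 1.05^d × (1 − c)

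| Assumed d | Interval | Falling, c = 20% | Falling, c = 30% | Rising first, c = 20% | Rising first, c = 30% |
|---|---|---|---|---|---|
| 15 min | 6.25 h | 20.7% | 31.0% | 19.0% | 29.1% |
| 30 min | 6.5 h | 21.5% | 32.0% | 18.0% | 28.3% |
| 1 h | 7 h | 22.9% | 34.0% | 16.0% | 26.5% |
| 2 h | 8 h | 25.7% | 37.8% | 11.8% | 22.8% |

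**Step 5: difference between arms.** Suppose one arm has d = 0 and the other d = 30 minutes. In the falling case the spurious difference is 21.5 − 20.0 = 1.5 points or 32.0 − 30.0 = 2.0 points. In the rising case it is 18.0 − 20.0 = −2.0 points or 28.3 − 30.0 = −1.7 points. With a one-hour difference, the falling case gives 2.9 or 4.0 points and the rising case −4.0 or −3.5.

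Every value of d, c and the rates of change is an assumption; the documents supply none of them.

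**The case against.** The strongest reply is that the arms probably start at nearly the same time. The scan runs alongside venous access, which usual-care patients also need before an intravenous load. The bolus is to follow at once when indicated, and usual care is described as equally prompt. UGFM treatment can also be read as starting with the scan, since patients are treated with a strategy and the scan is its first step; a patient below the threshold then has a start time. This stands as a reason to expect a small difference. It does not supply the missing definition, and it leaves patient-to-patient variation in place.

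Three stronger readings are tempting, and the documents do not support them:

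- **That the UGFM baseline was drawn after assignment.** A reader might infer this because the scan, an arm-specific step, coincides with collection of initial specimens. That phrase does not mention lactate. The Study Protocol section names lactate, times it at arrival for every patient and places assignment afterwards. Nothing says when usual-care specimens were drawn relative to assignment, so a contrast between arms would rest on silence. The sequence wording is loose, and no more than that.
- **That the delay went unrecorded.** The plan does not say that draw times or treatment-start times were captured. It does not say that they were not.
- **That the comparison is biased in a known direction.** No difference between arms is shown, and the table shows that its sign would depend on how lactate behaves before treatment.

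It can also be said that, with no formula given, clearance per hour is not excluded. That is true, but dividing by hours assumes linear decline. Under the exponential model, c = 20% gives 20.0/6 = 3.33 points per hour at six hours and 22.9/7 = 3.27 at seven, so the dependence on interval shrinks but remains.

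**Conclusion.** The mismatch holds on the plan's own wording. Lactate clearance runs for six hours plus an arrival-to-treatment time that has no stated limit, and its end depends on a treatment start that is not defined for UGFM. The interval therefore varies between patients and could differ by arm. That it did differ is not shown, and the parallel scan suggests any gap may be small.

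For an assumed 30-minute gap and six-hour clearance of 20% to 30%, the shift is about 1.5 to 2 points under exponential decline, and of similar size in the opposite direction if lactate first rises by 5% per hour. If the sponsor treats arrival and treatment start as the same moment, the interval is six hours and the problem disappears, but the text does not say so.

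This affects the reading of one outcome that does not determine the sample size. It is a cheap improvement.

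**What to change.** 1. Time the second lactate from one origin that does not depend on the arm. Six hours after the hour-0 sample fixes the interval for everyone. Six hours after randomisation leaves some variation between patients, but all of it arises before assignment.
2. Confirm that the baseline lactate is the pre-assignment hour-0 sample in both arms, and reconcile the passages on when specimens are collected.
3. Compare the arms on the second lactate with baseline lactate as a covariate, in place of an unadjusted test on clearance. Raw clearance can still be reported, with its formula stated.
4. Report the actual draw intervals by arm where draw times are available. Use the actual interval as a covariate only in a sensitivity analysis: it is determined after randomisation and may depend on the arm, so adjusting for it could remove part of the strategy's effect or add bias.

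The cost is a few sentences of protocol and SAP wording, draw times, and an outcome slightly less familiar than raw clearance. The document is written in the past tense, so sampling may already be complete. In that case item 1 is no longer available and draw times would have to be retrieved. Items 2 to 4 remain possible, and the intervals by arm would show whether the concern had any practical effect.

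### The 80% power rests on a 30% usual-care mortality labelled 90-day, but deaths are ascertained and compared at 30 days, with no 30-day rate or bridging reason given

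*Combined protocol and SAP*

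**What the plan says.** Under *Sample-size determination*, the usual-care rate comes from outside the trial: "According to the results of large trials of septic shock treatment", "the 90-day mortality was 30% in the usual-care group". From it, "we calculated that a sample of 254 patients would have a power of 80% to detect a relative reduction of 50% in risk", which the plan also expresses as "15 percentage points of absolute risk reduction", after allowing 5% for loss or withdrawal. The same paragraph continues: "The target number for primary outcome analysis would be 121 patients per" group.

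Under *Outcome Measurements*, the search for deaths is set at a different time point. "To identify the deceased patients for mortality analysis", records are searched or a telephone call is made "in every case at 30 days after the day of hospital presentation".

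Under *Statistical analysis*, the comparison matches that follow-up: "We used the Kaplan-Meier curve and the log-rank test to compare the 30-day mortality between the treatment arms". A chi-square test with odds ratio is planned for proportions in general. Tests are two-sided at 5%.

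The document describes no 90-day follow-up and no 90-day analysis.

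**The concern.** A power statement applies to a particular comparison. Here the control rate behind it is tied to day 90, while deaths are counted and compared at day 30. Cumulative mortality cannot fall over time, so in the population that the 30% describes, 30-day mortality is at most 30% and may be less. With a fixed relative reduction, a lower control rate means fewer deaths and less power. The plan neither gives a 30-day rate nor says why 30% should hold at day 30.

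A reader therefore cannot tell whether the 80% applies to the mortality comparison that will be reported. This matters most if the 30-day result is not significant, because the stated power then shapes how much reassurance or doubt is drawn from it. The validity of the comparison is not in question.

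Two related points are left open. The paragraph sizes a primary outcome without naming it, so 30-day mortality as primary is an inference: the sizing is on mortality, and 30 days is the only time point at which mortality is compared. The test is also unsettled. The number 121 fits a two-proportion calculation, but the log-rank test is the one named for 30-day mortality.

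**Working it through.** **Inputs from the plan.** Usual-care rate 30% (labelled 90-day); 50% relative reduction, so 15% in the ultrasound-guided group; two-sided 5%; 80% power; 1:1 allocation; 5% loss; 121 evaluable per group; 254 in total.

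**Reproducing the stated size.** Two-proportion formula, pooled variance under the null, unpooled under the alternative, no continuity correction:

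n = [1.960·√(2·p̄(1−p̄)) + 0.842·√(p₁(1−p₁) + p₂(1−p₂))]² / (p₁−p₂)²

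With p₁ = 0.30, p₂ = 0.15, p̄ = 0.225:

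n = [1.960 × 0.5906 + 0.842 × 0.5809]² / 0.15² = 120.5, so 121 per group, 242 in total.

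Loss allowance: 242 / 0.95 = 254.7, or 242 × 1.05 = 254.1; the plan has 254. Power at 121 per group is 80.2%. The arithmetic holds, and the 30% is the figure that produced the sample size.

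**Power if the 30-day rate differs.** The documents give no 30-day rate, so 20% to 35% is an assumed range. Settings: n = 121 per group, two-sided 5%, p₂ = p₁/2, interim look ignored.

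Power = Φ{ [(p₁−p₂)·√n − 1.960·√(2·p̄(1−p̄))] / √(p₁(1−p₁) + p₂(1−p₂)) }

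Example at 25% v 12.5%: (0.125 × 11 − 1.960 × 0.5520) / 0.5449 = 0.538, and Φ(0.538) = 70.5%.

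| Assumed 30-day usual-care rate | Two-proportion formula | Exact uncorrected chi-square | Simulated log-rank | Relative reduction detectable with 80% power (two-proportion) |
|---|---|---|---|---|
| 35% | 87.6% | 88.0% | 88.3% | about 45% |
| 30% | 80.2% | 80.9% | 81.0% | about 50% |
| 25% | 70.5% | 71.6% | 71.2% | about 55% |
| 20% | 58.7% | 59.7% | 59.4% | about 62% |

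The exact column enumerates both binomial distributions. The log-rank column uses 100,000 simulated trials per rate, with exponential times to death (an assumption) and censoring at day 30. The choice of test shifts power by about one point; the control rate shifts it by far more.

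**Where power reaches 80%.** With the 50% relative reduction kept, the rate needed is 29.9% by the two-proportion formula. At 29.5%, exact chi-square and simulated log-rank power are both 80.1%.

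**Holding the absolute difference instead.** At 25% v 10%, the 15 points are kept and two-proportion power rises to 87.1%. But 15/25 is a 60% relative reduction, a larger relative effect than the plan assumes.

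**The case against.** The strongest reply is that no loss of power has been shown. A control rate borrowed from other trials is always approximate. Population and setting matter as well as the day of follow-up, and the 30-day ceiling of 30% binds only in the population the figure came from. This trial's own 30-day rate could be 30% or more; at 40% v 20% the same formula gives 93%. The label may also be a slip, in which case the 80% is right. And any sample size solved for 80% power will sit at about 80% under its own inputs, so the thin margin is partly built in. All of this stands, and it is why the conclusion is that the stated power is unsupported, not that the trial is too small.

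A second reply is that 254 patients are enrolled, 127 per group, and every case is to be followed through records or by telephone. With no loss at all, power at 30% is 82.1% and the 80% point falls to 28.8%. That is correct, but it sets aside the plan's own 5% allowance, adds only about two points, and leaves the two time points unreconciled.

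A third is that a non-significant result should be read mainly from the estimate and its confidence interval. That is fair and limits the consequence. It does not excuse a power statement whose input belongs to a different time point.

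**Conclusion.** The concern holds. The 80% power is derived from a rate labelled 90-day, the mortality comparison described is at 30 days, and nothing in the document connects the two. The mismatch itself is plain from the text. Its size is not known: it depends on a 30-day usual-care rate that the plan does not give. Over the assumed 20% to 35%, two-proportion power for a 50% relative reduction runs from 58.7% to 87.6%. If 90-day is a labelling slip for 30-day, the 80% stands.

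The conclusion assumes that 30-day mortality is the unnamed primary outcome and that the relative reduction, not the absolute one, is the effect kept fixed. It is a point that should be fixed because a stated design figure lacks support; type I error and the validity of the comparison are untouched.

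**What to change.** In *Sample-size determination*, do one of the following.

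1. If 30% was meant as the 30-day rate, correct the label. The stated power then needs no change.
2. Otherwise, state the expected 30-day usual-care mortality, justified from an outside source and not from this trial's accumulating data, and restate power for the 30-day comparison. If the source supports 30% at day 30, saying so is enough. Possible wording: *We assume 30-day usual-care mortality of X% (source). With 121 evaluable patients per group, two-sided 5% and the two-proportion test, power for a 50% relative reduction is 87.6%, 80.2%, 70.5% or 58.7% if that rate is 35%, 30%, 25% or 20%; the relative reduction detectable with 80% power is about 45%, 50%, 55% or 62%.* If the log-rank test is the intended primary test, name it and use its figures, which differ by about one point.

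In either case, say whether 30-day mortality is the primary outcome referred to.

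The cost is one corrected label, or one or two sentences. Sample size and endpoint do not change. The only drawback is that the restated power may be less favourable.
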